6. TREATMENT OF STUDY PARTICIPANTS

6.1 DESCRIPTION OF STUDY VACCINES

The term 'study vaccine' refers to those vaccines provided by the Sponsor, which will be evaluated as part of the study objectives. The study vaccines specific to this study are described below.

Study Vaccines

COVISHIELD Prime cohort	Test vaccine	COVOVAX [SARS-CoV-2 recombinant spike protein nanoparticle vaccine (SARS-CoV-2 rS) with Matrix-M1 TM adjuvant]
	Control	Covishield TM
COVAXIN Prime cohort	Test vaccine	COVOVAX [SARS-CoV-2 recombinant spike protein nanoparticle vaccine (SARS-CoV-2 rS) with Matrix-M1 TM adjuvant]
Time conort	Control	Covaxin TM

6.1.1 Test vaccine:

COVOVAX [SARS-CoV-2 recombinant spike protein nanoparticle vaccine (SARS-CoV-2 rS) with Matrix-M1TM adjuvant] is available as a ready to use liquid formulation in a 10-dose (5.0 mL) vial. Each dose of 0.5 mL contains 5 µg antigen and 50 µg Matrix-M1 adjuvant. The other ingredients are 25 mM phosphate buffer (pH 7.2), 300 mM sodium chloride, and 0.01% (v/v) polysorbate 80.

- Manufacturer: Serum Institute of India Pvt. Ltd. (SIIPL)
- **Formulation**: Ready to use liquid formulation in a 10-dose vial.
- Route of administration: Intramuscular
- **Site of injection:** Deltoid muscle
- **Dose:** 0.5 ml containing 5 μg antigen and 50 μg Matrix-M adjuvant
- Dose schedule: Single dose on Day1

CONFIDENTIAL Page 40 of 94

6.1.2 Comparator product [Covishield TM for Covishield prime cohort and Covaxin for Covaxin prime cohort]:

Version: 4.0 Dated 21 Apr 2022

CovishieldTM:

One dose (0.5 ml) contains:

ChAdOx1 nCoV- 19 Corona Virus Vaccine (Recombinant) 5 × 10¹⁰ virus particles (vp)

*Recombinant, replication-deficient chimpanzee adenovirus vector encoding the SARS-CoV-2 Spike (S) glycoprotein. Produced in genetically modified human embryonic kidney (HEK) 293 cells.

• Manufacturer: Serum Institute of India Pvt. Ltd.

• Formulation: Ready to use formulation in multi-dose glass vials

• Route of administration: Intramuscular

• **Site of injection:** Deltoid muscle

• **Dose:** 0.5 ml.

• **Dose schedule:** Single dose on Day 1.

Covaxin®:

Each dose of 0.5mL contains:

Ingredient	Quantity
Whole Virion, Inactivated Coronavirus (SARS-CoV-2) Antigen	6 μg
(Strain: NIV-2020-770)	
Aluminium Hydroxide Gel equivalent to Al+++	0.25 mg
TLR7/8 Agonist	15 µg
2-Phenoxyethanol	2.5 mg
Phosphate Buffered Saline	q.s. to 0.5 mL

• Manufacturer: Bharat Biotech International Limited

• Formulation: Ready to use formulation in glass vials

• Route of administration: Intramuscular

• **Site of injection**: Deltoid muscle

• **Dose**: 0.5 ml.

• **Dose schedule**: Single dose on Day 1.

CONFIDENTIAL Page 41 of 94

6.2 PRECAUTIONS TO BE OBSERVED IN ADMINISTRATING STUDY VACCINES

Version: 4.0 Dated 21 Apr 2022

Prior to vaccination, participants must be determined to be eligible for study vaccination and it must be clinically appropriate in the judgment of the investigator to vaccinate.

Study vaccines should not be administered to individuals with known hypersensitivity to any component of the vaccines.

Standard immunization practices are to be observed and care should be taken to administer the injection intramuscularly. Before administering the study vaccine, the vaccination site is to be disinfected with a skin disinfectant (e.g., 70% alcohol). Allow the skin to dry. DO NOT inject intravascularly.

As with all vaccines, appropriate medical treatment (like adrenaline 1:1000, anti-histamine (diphenhydramine), corticosteroids (hydrocortisone) and resuscitation equipment etc.) must be available at the site, and staff and supervision must be readily available in case of rare anaphylactic or any severe allergic reactions following administration of the study vaccine.

Prompt use of resuscitation measure can be lifesaving and must be implemented at the first suspicion of anaphylaxis.

6.3 PREPARATION AND ADMINISTRATION OF THE STUDY VACCINE

Study vaccines are available as a ready to use vial / ampoule and does not need any reconstitution. A vial / ampoule will be removed from cold storage and inspected to confirm the absence of particulate materials and 0.5 mL volume from vial / ampoule will be withdrawn using needle and syringe and injected intramuscularly.

Study vaccine should be visually inspected before administration and in the event of any foreign particulate matter and/or any unusual appearance of the study vaccine, vial / ampoule will be set aside and replacement vial / ampoule should be used.

The study vaccine will be administered as per randomization schedule via intramuscular injection on Day 1. Preferred site of injection is deltoid muscle. The study vaccines are supplied as 10-dose vials for COVOVAX, and single dose ampoule / multi-dose vials for control vaccine. The used vial / ampoule will be kept securely at site for accountability by study monitor.

The investigator or designee will be responsible for oversight of the administration of vaccine to participants enrolled in the study according to the procedures presented in this study

CONFIDENTIAL Page 42 of 94

protocol. All vaccines will be prepared and administered only by designated personnel who are qualified to perform that function.

Version: 4.0 Dated 21 Apr 2022

Study vaccine to be administered to the participants must be stored in a safe and locked place with no access by unauthorized personnel.

6.4 VACCINE SUPPLY, LABELLING, STORAGE, ACCOUNTABILITY AND DISPOSAL

The sponsor will ensure the following:

- Appropriate supply of the study vaccines;
- Appropriate labeling of all study vaccines that complies with regulatory requirements.

The investigator must ensure the following:

- Availability of appropriately trained site staff to manage vaccine supply, accountability, preparation and administration.
- Acknowledge receipt of the study vaccines by site staff, including confirmation that the vaccines:
 - were received in good condition;
 - remained within the appropriate temperature range during shipment from the sponsor to the investigator's designated storage location;
 - have been confirmed by the sponsor as authorized for use
- Proper storage of the study vaccines, including:
 - storage in a secure, locked, temperature-controlled location;
 - proper storage according to the instructions specified on the labels;
 - appropriate record keeping and inventory of the study vaccines, including regular documentation of adequate storage temperature
- Appropriate use of the study vaccines, including:
 - use only in accordance with the approved protocol;
 - proper handling, including confirmation that the vaccine has not expired prior to administration:
 - appropriate documentation of administration of vaccines to study participants including:

CONFIDENTIAL Page 43 of 94

 Date, dosage, batch number, screening number assigned to participants, and time of vaccine administration. This information will be maintained in an accountability log that will be reviewed by the site monitor;

Version: 4.0 Dated 21 Apr 2022

- Proper reconciliation of all study vaccines received from the sponsor. Reconciliation is defined as maintaining records of which and how many vaccines were received, which vaccines (and volume thereof) were administered to participants, and which vaccines were destroyed at the site.
- Vaccine will be either destroyed at site after sponsor approval or can be returned back to sponsor. Site will provide adequate documentation of destruction in the former case.

The study vaccines will be stored at $+2^{\circ}$ C to $+8^{\circ}$ C in a secure refrigerator. The storage temperature of the vaccines will be monitored daily with temperature monitoring devices and will be recorded.

Vaccines that have been stored differently from the manufacturer's instructions must not be used unless the sponsor provides written authorization for use. Any temperature deviation, i.e. temperature outside the range, must be reported to the sponsor as soon as detected. Following the exposure to such a temperature deviation, vaccines will not be used until written approval has been given by the sponsor. Expired vaccines must not be administered.

In the event that the use cannot be authorized, the sponsor will make every effort to replace the vaccine supply. Monitoring of vaccine accountability will be performed by the study monitor during site visits and at the completion of the trial.

7. STUDY PROCEDURES

7.1 GENERAL CONSIDERATIONS

The study will be initiated only after approvals from each site's Institutional ethics committee (IEC) and the DCGI have been obtained.

The schedules of evaluations and procedures that must be performed at specific time points are described in the following sections and in Tables 1: Schedule of study events.

At each visit participants need to be counselled thoroughly to follow all the standard measures like wearing mask, social distancing, regular hand washing, using of hand sanitizer etc. as per the health authority guidelines to prevent getting infected with SARS CoV-2.

CONFIDENTIAL Page 44 of 94

7.2 STUDY VISITS

Visit #1 – Screening, Randomization and Vaccination

Potential participants will be informed about the scope of the study and the possibility of their inclusion in the study. If they are willing to participate, informed consent will be obtained. A signed (or thumb print with witness signature) and dated informed consent must be obtained by the principal investigator (PI) or the designee before initiating any study specific procedures. The informed consent document used for the purpose must be approved by respective site IEC. The process of obtaining informed consent should be documented in the source documents in addition to maintaining the original signed and dated informed consent at the site. A copy of the consent form will be given to the participants.

Version: 4.0 Dated 21 Apr 2022

The participants will be screened for eligibility by the PI / designated site staff under the direction of the PI after the informed consent process has been completed. All participants screened for the study will be assigned a screening number.

All participants who have consented will be evaluated for eligibility.

The following procedures will be completed for each participant to confirm eligibility for the study:

- Demography (Age, sex, height and weight)
- Details of COVID-19 vaccination (Name of vaccine and dates of vaccination Dose 1 and Dose 2)
- Medical History (significant past and concurrent conditions, family history, history of allergies and vaccinations, history of COVID-19)
- Complete physical Examination [general, respiratory, cardiovascular system, and central nervous system] including vital signs measurements (temperature, resting blood pressure, pulse and respiratory rate)
- Relevant prior and Concomitant medications
- In case of female participants of child bearing potential, urine pregnancy test (UPT) will be performed prior to randomization.

The participants who are ineligible for the study or not randomized will be documented as screen failures on the Screening Log and/or eCRF. The reason for screen failure must be documented.

CONFIDENTIAL Page 45 of 94

A complete review of inclusion/exclusion criteria will be conducted. Participants who satisfy

Version: 4.0 Dated 21 Apr 2022

all inclusion criteria and none of the exclusion criteria will be enrolled.

Randomization:

The eligible participants will be randomized on the same day. The eligible participants will be

randomized via an Interactive Web Response System (IWRS).

If for any reason, after signing the informed consent form, the participant (who has passed

screening) fails to be randomized, the reason for not being randomized should be recorded in

source documents.

Blinding:

The study is designed as an observer-blind study. The study participants and the study

personnel responsible for the evaluation of any study endpoints (e.g. safety) will be unaware

which study vaccine is administered. At each site, only designated study personnel will be

involved in getting randomization code by accessing IWRS, vaccine preparation and

administration. The unblinded personnel involved in study vaccine preparation and

administration will not participate in any of the study end-point evaluations. All other site

personnel will remain blinded to the treatment allocation.

The sponsor personnel involved in the study will also remain blinded until 28 days after the

booster dose. At the interim analysis of data at 28 days after study vaccination, the sponsor

personnel will become unblinded to group-wise data. Individual level blinding will still be

maintained for the sponsor personnel until study completion i.e. final database lock. The CRO

will designate an unblinded monitor(s) and a statistician who may be able to access the subject

level unblinded data as per the need. Other CRO personnel working on the trial will remain

blinded.

The laboratories involved in the immunological testing will be blinded to the treatment

allocation.

Prior to Randomization and Vaccination:

If the participant meets all the eligibility criteria, a swab from nasopharynx /nose and/or throat

will be collected for RT-PCR testing to detect SARS-CoV-2 infection to assess baseline status.

Approximately 10 ml blood will be collected from participants for anti-S IgG and neutralizing

antibody assessment prior to vaccination on Day 1. Additionally, up to 20 ml blood sample

CONFIDENTIAL Page 46 of 94

-

Version: 4.0 Dated 21 Apr 2022

may be collected from subset of 36 participants (18 from each of the two prime cohorts) for assessment of CMI responses.

Study Vaccination: The eligible participant will receive 0.5 ml of either COVOVAX or Control vaccine as per the randomization schedule.

Post - Vaccination Activities:

The participants will be observed closely for at least 30 minutes following vaccination, with appropriate medical treatment readily available in case of a rare anaphylactic reaction following the administration of vaccine. After 30 minutes (+15 minutes) post vaccination, any unsolicited AEs and Vitals (temperature, resting blood pressure, pulse and respiratory rate) will be recorded.

The participants will receive a digital thermometer, measuring scale and a diary. These participants will be trained by the site personnel for recording and documenting any solicited AEs within 7 days after vaccination and any other AEs they may experience until 28 days after vaccination and concomitant medications they may use in the diary. The participants will be informed to visit the site on Day 29 and carry this completed diary at the time of visit.

The investigator or a delegate should ensure that all information is recorded in the source documents and accurately transcribed in the eCRF as soon as possible after the participant's visit has been completed.

The participant will be reminded to contact the site if there is any health problem / illness or if they have any questions and to return to the clinic on Day 29.

Visit #2 (Day 29 [+7]):

Study participants will return for follow-up evaluations to the clinical study site 28 days after the vaccination. At this visit, investigator or delegate will perform the following procedures and evaluations in the following order:

- 1. Review and retrieval of diary card records
- 2. Assessment of any ongoing solicited AEs (note that all ongoing solicited AEs must be followed up by site staff until resolution)
- 3. Medical interview of participant to assess any unsolicited AEs/SAEs/AESI since previous study visit
- 4. Collection of concomitant medications and vaccinations history

CONFIDENTIAL Page 47 of 94

- 5. Targeted physical examination including assessment of vital signs
- 6. Collection of blood sample (approximately 10 mL) for anti-S IgG and neutralizing antibody assessment. Additionally, up to 20 ml blood sample may be collected from subset of 36 participants (18 from each of the two prime cohorts) for assessment of CMI responses.

Occurrence of COVID-19 disease: If any of the study participants experience signs/symptoms suggestive of COVID-19 or history of exposure to a confirmed case of COVID-19, RT-PCR test will be performed. If the participant is confirmed with COVID-19 after the study vaccination, this will be documented in the source and eCRF.

Visit # 3 (Day 91 [+7]):

Study participants will return for follow-up evaluations to the study site 90 days following study vaccination. At this visit, investigator or delegate will perform the following procedures and evaluations in the following order:

- 1. Medical interview of participant to determine if any SAE/ AESI occurred and if any concomitant medications were taken/ received since the last study visit.)
- 2. Targeted physical examination including assessment of vital signs.
- 3. Collection of blood sample (approximately 10 mL) for anti-S IgG antibody assessment.

The investigator or a delegate should ensure that all information is recorded in the source documents and accurately transcribed in the eCRF as soon as possible after the participant's visit has been completed.

The participant will be reminded to contact the site if there is any health problem / illness or if they have any questions and to return to the clinic on Day 181.

Visit #4 (Day 181 [+14]): End of study visit

Study participants will return for follow-up evaluations to the study site at 6 months following vaccination. At this visit, investigator or delegate will perform the following procedures and evaluations in the following order:

- 1. Medical interview of participant to determine if any SAEs/ AESI occurred and if any concomitant medications or vaccines were taken/ received since the last study visit.)
- 2. Targeted physical examination including assessment of vital signs.

CONFIDENTIAL Page 48 of 94

3. Approximately 10 ml blood will be collected from participants for anti-S IgG and neutralizing antibody assessment. Additionally, up to 20 ml blood sample may be collected from subset of 36 participants (18 from each of the two prime cohorts) for assessment of CMI responses.

The investigator or a delegate should ensure that all information is recorded in the source documents and accurately transcribed in the eCRF as soon as possible after the participant's visit has been completed.

In case there are no ongoing SAEs, after this visit, the participation in the study will be completed. Source records will be completed and all information will be recorded in the eCRF (including "end of study" page).

Unscheduled Visits

Unscheduled visits may be performed at participant's requests or directly by the study site when the investigator or a delegate considers it necessary for diagnosis and/or management of a finding or an AE. All unscheduled visits will be recorded in source and eCRF.

7.3 TESTING FOR COVID-19 DURING THE STUDY PERIOD:

If the participant presents with qualifying symptoms of suspected COVID-19 disease [Appendix II, Table 1] OR history of contact with a confirmed COVID-19 positive case then a swab from nasopharynx / nose and/or throat will be collected for RT-PCR testing for SARS-CoV-2 infection.

At the COVID-19 testing visit, a swab from nasopharynx /nose and/or throat, vital signs and other clinical data will be taken. Symptomatic cases will be managed as per national guidelines.

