4. STUDY DESIGN

This is a Phase 3, observer-blinded, randomised, active controlled study in adults ≥ 18 years of age in India who have already received primary vaccination against COVID-19 at least 6 months ago (6 months / 180 days from the second dose), to evaluate the immunogenicity and safety of the COVOVAX booster dose in comparison with the control vaccine.

Version: 4.0 Dated 21 Apr 2022

A total of 372 eligible participants of \geq 18 years of age who have completed primary 2 dose schedule of COVID-19 vaccination at least 6 months ago will be enrolled in this study in 2 cohorts of 186 participants each with 1:1 allocation to COVOVAX or control vaccine. Two cohorts of 186 participants each will be as below:

- **COVISHIELD Prime cohort:** Primary vaccination with two doses of COVISHIELD
- **COVAXIN Prime cohort:** Primary vaccination with two doses of COVAXIN

All eligible participants (n=372) will receive a single dose of 0.5 mL of either COVOVAX or Control vaccine on Day 1 as per randomization. Post vaccination site visits are planned on Day 29, Day 91, and Day 181.

Treatment allocation:

COVISHIELD Prime cohort	COVOVAX	93
	Covishield	93
COVAXIN Prime cohort	COVOVAX	93
	Covaxin	93

Approximately 10 ml blood sample will be collected at baseline (Day 1), Day 29, Day 91 and Day 181. Additionally, up to 20 ml blood sample may be collected from subset of 36 participants (18 from each of the two prime cohorts) for assessment of CMI responses at baseline, Day 29 and Day 181.

CONFIDENTIAL Page 36 of 94

Table 1: Schedule of study events

Visit Number	1	2	3	4
Visit time and window	Day 1	Day 29 (+7)	Day 91 (+7)	Day 181 (+14)
Informed Consent	X		NA	En
Demographic Data	X		NA	
Medical History including details of COVID-19 Vaccination	X		NA	
General Physical Examination & vital signs	X	Xa	Xª	Xa
Urine pregnancy test ^b	X	20.0	NA	
Inclusion/Exclusion Criteria	X	NA		
Randomization	X	NA		
Nasopharyngeal /Nose and/or throat swab for RT-PCR	X	Xc		
Blood collection for immunogenicity assessments	X	x x x		X
Study Vaccination	X	NA		Apa
30-Minute Post-Vaccination Assessment	X	NA		
Recording of solicited AEs		7 days post- cination		
Recording of unsolicited AEs	2.00	ough 28 days post- vaccination		NA
Reporting of SAEs, AESI	Throughout the study			
Recording of concomitant medications and vaccinations ^d		Throughout the study		

CONFIDENTIAL Page 37 of 94

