a. A targeted physical examination (only at post vaccination visits) will be performed if there has been any AE reported since the previous visit that has not already been recorded and closed within unscheduled visits

b. Only among female participants of child bearing potential.

C. Post-vaccination: If the participant presents with qualifying symptoms of suspected COVID-19 disease [Appendix II, Table 1] OR history of contact with a confirmed COVID-19 positive case then a swab from nasopharynx / nose and/or throat will be collected for RT-PCR testing for SARS-CoV-2 infection.

d. Beyond Day 29, only the concomitant medications indicated for SAEs and AESI, if any will be recorded

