7.6.2 Concomitant Medications and Vaccines

At each study visit, the investigator/designee will ask the participants about any prescription or over-the-counter medication(s) taken since the last visit. Any medications taken at any time during the study period must be recorded on source documents and the eCRF with trade and/or generic name, indication, dose, start and end dates until Day 29. Beyond Day 29, only medications taken for SAE / AESI will be recorded.

Any treatments and/or medications specifically contraindicated, e.g., any investigational or non-registered product, any immunosuppressant and immune-modifying drug including systemic steroids, any immunoglobulin and blood product should be checked at each study visit subsequent to the study vaccination. If any become applicable during the study, it will not

CONFIDENTIAL Page 51 of 94

require withdrawal of the participant from the study but may determine a participant's evaluability in the per-protocol analysis.

Any vaccine not foreseen in the study protocol in the period starting at Visit 1 (Day 1) and ending at end of study visit must be recorded in the eCRF.

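### The visit lists do not carry out the rule to record non-study vaccines: for anyone who attends Visit 3, none asks about vaccines given between Day 29 and Day 91

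*Protocol*

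**What the plan says.** **The general rule.** Protocol section 7.6.2 has a paragraph on vaccines alone. It takes in every non-study vaccine from the first visit onwards, and its sentence closes: "ending at end of study visit must be recorded in the eCRF". The schedule of events (section 4, Table 1) has a row headed "Recording of concomitant medications and vaccinations", marked as running throughout the study.

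**The visit lists (section 7.2).**
- Visit 2 (Day 29): "Collection of concomitant medications and vaccinations history".
- Visit 3 (Day 91): the interview covers SAEs and AESIs and asks "if any concomitant medications were taken/ received since the last study visit".
- Visit 4 (Day 181): the interview asks "if any concomitant medications or vaccines were taken/ received since the last study visit".

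**The footnote.** Footnote d to the Table 1 row reads: "Beyond Day 29, only the concomitant medications indicated for SAEs and AESI, if any will be recorded".

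**The use made of the data.** Estimands 4 to 9 (section 3.2) target antibody levels without the influence of other vaccines. They cover anti-S IgG up to Day 181, including Day 91, and neutralizing antibodies up to Day 181. The Per Protocol definition (section 10.5.5) drops data from time points after a vaccine that interferes with assessing immunogenicity.

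**The concern.** The exclusion of post-vaccine data works only if the site learns that a vaccine was given, and when. Two visits ask about vaccines by name. The one between them does not, and the last one looks back only as far as the visit before it. A COVID-19 vaccination in that interval that nobody mentions leaves a raised titre in the Day 91 GMT, in the Day 181 GMT, or in both. Persistence then looks better than it is. The analyst cannot repair this later, because nothing in the data shows that a vaccination was missed.

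Footnote d adds a second difficulty. It sits on a row that covers medications and vaccinations together, and it says that only certain medications are recorded after Day 29. Site staff could take it to mean that vaccine recording stops there, which would contradict section 7.6.2.

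**Working it through.** The plan states no figure to reproduce. The check sets the instructions side by side by interval and then sizes one missed vaccination.

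**Coverage by interval**

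| Interval | Length | Vaccine question in a visit list | Duty to record |
|---|---|---|---|
| Day 1 to Day 29 | 28 days | Yes, Visit 2 | Yes, 7.6.2 and Table 1 |
| Day 29 to Day 91 | 91 − 29 = 62 days | None, if Visit 3 is attended | Yes, 7.6.2 and Table 1 |
| Day 91 to Day 181 | 181 − 91 = 90 days | Yes, Visit 4 | Yes, 7.6.2 and Table 1 |

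The interval without a question is 62/180 = 34% of follow-up, and 62/90 = 69% of the time before the Day 91 sample. If Visit 3 is missed, the Visit 4 wording reaches back to Day 29 and the gap closes.

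**Whether another instruction supplies the question**
- The diary does not. It is retrieved at Visit 2.
- The question that section 7.6.2 prescribes for each visit concerns prescription and over-the-counter medication.
- The check of contraindicated treatments at each visit gives as examples investigational or non-registered products, immunosuppressive and immune-modifying drugs, immunoglobulins and blood products. Licensed vaccines are not among them.
- Section 7.6.1 counts vaccines as medications when defining prior therapy. If that meaning carried over to Visit 3, the question would cover vaccines. But the Day 29 limit on medications, in footnote d and in 7.6.2, would then cover them too, against the separate vaccine paragraph of 7.6.2. If it does not carry over, Visit 3 omits vaccines. Either reading leaves something to correct.

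**Size of one missed vaccination**

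Inputs: n = 79 evaluable per arm (section 10.4); fold rise F, which the documents do not give for a further dose 1 to 3 months after the study booster and which is therefore assumed; k missed participants. For a simple geometric mean, with the full rise present at the draw:

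relative change in GMT = exp(k × ln F / n) − 1

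- F = 10, k = 1: exp(2.3026/79) − 1 = exp(0.0291) − 1 = 3.0%
- F = 10, k = 2: exp(0.0583) − 1 = 6.0%
- F = 2 (the protocol's own responder threshold), k = 1: exp(0.6931/79) − 1 = exp(0.0088) − 1 = 0.9%

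These are illustrations. The documents give no uptake, so no expected bias can be stated.

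**The case against.** A reader might infer that vaccinations between Day 29 and Day 91 go uncollected. The documents do not support that. Section 7.6.2 makes recording mandatory up to the end-of-study visit, the Table 1 row runs throughout the study, and section 7.1 says that procedures are set out in the sections and in Table 1. The visit lists are therefore not the only instruction. A reader might also infer that the periods before and after Day 91 follow different rules. They do not: one recording duty and one Per Protocol rule cover both, and only the interview wording differs.

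It is fair to add that footnote d names medications and not vaccines, and that 7.6.2 shows how it was probably meant. Planning a COVID-19 booster during the study is an exclusion criterion (section 5.2), so uptake should be low. Both arms get the same questions from blinded staff, so nothing points to a difference in ascertainment between arms. Estimands 6 to 9 are reported descriptively, and no hypothesis test is set for Day 91 or Day 181.

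A reader might size the bias with the 61.2-fold rise in anti-S IgG quoted in section 2.4.4. That figure does not transfer. It compares titres before and after a booster given about 6 months after priming, whereas here everyone has already been boosted on Day 1.

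All of this limits the severity. What it does not supply is the missing question. A duty to record applies only to what the site finds out.

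**Conclusion.** The point holds as a minor inconsistency that touches secondary endpoints only. The recording rule covers the whole study, but for participants who attend Visit 3 no visit list puts it into practice for Day 29 to Day 91, and footnote d is open to a reading that conflicts with section 7.6.2. The results exposed are the Day 91 and Day 181 GMTs under Estimands 4 to 9. One unreported COVID-19 vaccination among 79 would raise an arm's GMT by about 3%, assuming a 10-fold rise fully expressed at the draw and a simple geometric mean. A smaller rise gives less. How many such vaccinations would occur is unknown, and the booster exclusion makes a low number likely. The co-primary analyses at Day 29 are not affected, because Visit 2 collects vaccinations for the period that matters to them.

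**What to change.** 1. Section 7.2, Visit 3, item 1: ask about *concomitant medications or vaccines* since the last study visit, matching Visit 4.
2. For participants already past Visit 3: word the Visit 4 vaccine question as *since Visit 2 (Day 29)*, so that the interval is asked about before they leave the study.
3. Table 1, footnote d: state that the limit does not apply to vaccines, which are recorded with dates to the end of the study as in section 7.6.2.

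The cost is a few words in two sections and one question at an existing visit. Section 7.6.2 already requires vaccines to be entered in the eCRF, so no new visit or sample is needed.
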